9.0 Vulnerable Populations

No vulnerable populations will be recruited.

10.0 Local Number of Participants

We will recruit up to 120 smokers in order to complete at least 30 participants 20 achieving complete abstinence.

11.0 Local Recruitment Methods

11.1 Recruitment Process

Cigarette smokers will be recruited through the University of Minnesota Tobacco Research Programs. A variety of media will be used that will foster the recruitment across a spectrum of age, education and socioeconomic status, and race/ethnicity.

Cigarette smokers will contact the Tobacco Research Programs and will be pre-screened for eligibility over the telephone or in REDCap. During this pre-screening, information will be obtained on where the subject heard about the study, their geographic location, and basic demographics. This data will provide information on the primary media avenue, radio or television station, advertisement placements, internet location or domain responsible for recruiting subjects. We will use this information in our recruitment efforts.

11.2 Source of Participants

Primary recruitment via advertisements from Minneapolis-St. Paul metro area.

11.3 Identification of Potential Participants

Participants will self-identify first in response to advertisements and contact the study coordinator. Then, they will be screened over the phone or online for eligibility.

11.4 Recruitment Materials

Subjects will be recruited through printed flyers and advertisements through a variety of media outlets and the internet.

11.5 Payment

Subjects will receive \$25 for screening, \$30 for the Baseline and Intervention visits (\$20 for the visit and \$10 for transportation expenses). Those who consent to the blood draw will receive an additional \$20 for each blood draw. In order to maximize overall compliance, participants will be paid a \$600 bonus,). Subjects will be told that the bonus is contingent on compliance and this will be monitored via their daily ITR responses, product accountability, completion of forms, and submission of biological samples, and $CO \leq 6$ ppm. The maximum amount they can earn is \$925.

12.0 Withdrawal of Participants

12.1 Withdrawal Circumstances

If a participant is unable to achieve cessation (confirmed biologically either via CO or urine) within the first two weeks of the study, the participant will be withdrawn. Additionally, a study participant may be discontinued from the study if investigators determine that this is the best decision in order to protect his/her safety. If a participant either withdraws from the study or the investigators decide to discontinue a participant due to an adverse event (AE) or serious adverse event (SAE), the participant will have appropriate follow-up assessments and if necessary, referrals will be made for medical care. The participant experiencing an AE/SAE will be followed until the problem resolves, stabilizes, or is clearly unrelated to the study product. Any AE that remains open will be reviewed and closed at the Week 10 follow-up interview.

For the participant's protection, they will be withdrawn immediately from the study if any of the following occur:

- 1) Cardiovascular disease (CVD) event: Typically includes MI (heart attack), PTCA (angioplasty/stenting), bypass surgery, stroke, or peripheral vascular disease. Less common CVD problems would be new cardiac arrhythmias (e.g., new atrial fibrillation) or new valvular disease (e.g., mitral or aortic regurgitation).
- 2) DVT/PE (deep vein thrombosis/pulmonary embolism, i.e., blood clots in the venous system).
- 3) Suicide Attempt: A participant will be withdrawn if he/she attempts suicide at any time during participation in the study.
- 4) Psychiatric Hospitalization: A participant will be withdrawn if he/she is hospitalized for psychiatric reasons at any time during participation in the study.
- 5) Pregnancy: If a participant becomes pregnant, she will be immediately withdrawn from the study. In addition, the licensed medical professional will follow-up after delivery to ask questions about the health of the baby.
- 6) Expired breath carbon monoxide increase: A participant will be withdrawn from the study if the average of the 2 (or 3) CO readings is 100 ppm or greater.

- 7) **Respiratory Illness Event:** A participant will be withdrawn if they develop a severe (hospitalized or the symptom had a significant impact on his/her activities) respiratory illness that is related or possibly related to the SREC product as determined by the licensed medical professional.

The following will be monitored and can lead to the participant being withdrawn by the Principal Investigators or Medical Monitor:

- 1) **Blood pressure (BP) or heart rate (HR) changes:** If any of the following occur post-enrollment:
 - 1) BP is at or above 160 systolic/100 diastolic; 2) BP is below 90 systolic/50 diastolic and the participant is experiencing symptoms listed on the 'Blood Pressure and Heart Rate Symptom Checklist'; 3) HR is at or above 105 bpm; 4) or below 45 bpm and the participant is experiencing symptoms listed on the 'Blood Pressure and Heart Rate Symptom Checklist'.
- 2) **Medication changes:** If a participant begins taking any of the exclusionary medications or other medications that could potentially have a smoking-drug interaction post- enrollment, the licensed medical professional will determine how best to monitor and minimize potential risks (including withdrawal if warranted). We will also recommend that a letter be provided to the participant to give to their physician (with their consent) making them aware of the potential changes in smoking that could occur because of participation in the study.
- 3) Any hospitalization or debilitation in which participation in the study could be detrimental to the recovery process. This will be self-reported by the participant and reviewed by the investigators and medical professional to determine if continued participation in the study is appropriate.
- 4) If a participant is behaving in an inappropriate or threatening manner, admits to lying about eligibility criteria, including omitting previous medical diagnoses and medications, is participating in other smoking research studies that could affect the primary outcome measures, does not follow study instructions, etc., then he/she can be withdrawn at the investigators' discretion.
- 5) If there is reason to believe the participant is sharing large quantities of the study product with other people.

If a participant chooses to withdraw from the study at any time, we will ask them to return to the clinic to return study product and to receive their final study payment.

12.2 Withdrawal Procedures

Subject will be informed about the withdrawal at the visit and data collection will stop.

12.3 Termination Procedures

No additional procedures will be conducted if subjects are withdrawn.

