13. Smoking and Medications: Quitting smoking can greatly benefit participants' health. However, changes in smoking can lead to changes in how well some medications work. Participants should disclose all medications they are taking. We also recommend that participants discuss any planned or actual changes in how much they smoke with their doctor, especially if they are taking any medications for psychiatric, cardiovascular, or other serious diseases.
14. Unforeseen risks: There may be additional unforeseen short and long-term risks of participation.

Because smoking causes a multitude of diseases, if at any time the smoker wants to quit smoking, this decision will be encouraged and supported. At the end of study participation, subjects will be strongly encouraged to stop use of all tobacco products and to set a quit date and provided with a treatment resources and referral to different treatments.

13.2 Reproduction Risks:

Pregnant women will not be recruited. If participants choose to be sexually active, they should use an appropriate "double barrier" method of birth control (such as female use of a diaphragm, intrauterine device (IUD), or contraceptive sponge, in addition to male use of a condom) or the female should be using prescribed "birth control" pills, injections, or implants. Female participants with child-bearing potential will be tested for pregnancy at the baseline visit and monthly thereafter, if applicable. If a participant becomes pregnant during the study, she will be withdrawn from the study. Approximately 30 days after being withdrawn or having a positive pregnancy test, the research staff will call the

participant to confirm her due date. The licensed medical professional will follow-up with the participant after delivery to ask questions about the baby's health.

13.3 Risks to Others:

Second-hand exposure from SREC or usual brand cigarettes may be a risk to others.

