 - The 'Adverse Event Log' and 'Blood Pressure and Heart Rate Symptom Checklist' will be completed if an automatic and subsequent manual blood pressure measurement during the same visit is below 90 systolic or 50 diastolic and the participant is experiencing symptoms listed on the 'Blood Pressure and Heart Rate Symptom Checklist.'
- **Heart Rate:**
 - The 'Adverse Event Log' and 'Blood Pressure and Heart Rate Symptom Checklist' will be completed if an automatic and subsequent manual heart rate measurement during the same visit is at or above 105 bpm.
 - The 'Adverse Event Log' and 'Blood Pressure and Heart Rate Symptom Checklist' will be completed if an automatic and subsequent manual heart rate measurement during the same visit is below 45 bpm and the participant is experiencing symptoms listed on the 'Blood Pressure and Heart Rate Symptom Checklist.'

Adverse Events Communicated by Participants

The occurrence of AEs will be sought by non-directive questioning of the participant at each visit during the study. AEs also may be detected when the participant volunteers them during or between visits or through physical examination, laboratory test, or other assessments.

Review and Reporting of Adverse Events and Serious Adverse Events

Co-Principal Investigators with oversight from [name]. (Medical Monitor) and [name] (Nurse Practitioner) will review all AEs and assess whether they are related to the study product.

PROTOCOL TITLE: Biomarkers in SREC Users

VERSION DATE: 03/13/2024

An AE is defined as the appearance or worsening of any undesirable sign, symptom, or medical condition occurring after starting the study procedures even if the event is not considered to be related to the study product. Medical conditions/diseases present before starting the study are only considered adverse events if they worsen after starting the study product. Abnormal laboratory values or test results constitute adverse events only if they induce clinical signs or symptoms, are considered clinically significant, or require therapy; there are no plans for active monitoring of laboratory tests as part of this project. Withdrawal symptoms are considered adverse event if the symptom had a significant impact on the participant's daily life, caused a major disruption of functioning, or took any medication for it.

To the extent possible, each adverse event will be evaluated to determine:

1. the severity grade (mild, moderate, severe)

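### Participants withdrawn by the investigators without an AE or pregnancy, chiefly for not quitting by week 2, have no scheduled safety contact in the 4-week SAE window after product stop

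*Combined protocol and SAP*

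**What the plan says.** Two short sections govern what happens at withdrawal. Section 12.2: "Subject will be informed about the withdrawal at the visit and data collection will stop". Section 12.3: "No additional procedures will be conducted if subjects are withdrawn". Neither refers to any other section.

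Section 12.1 makes one withdrawal routine and mandatory: a participant who has not achieved biologically confirmed cessation "within the first two weeks of the study, the participant will be withdrawn". It also lists discretionary grounds, for example "If there is reason to believe the participant is sharing large quantities of the study product with other people".

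Follow-up after withdrawal appears in three other places:

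- Section 12.1: "If a participant either withdraws from the study or the investigators decide to discontinue a participant due to an adverse event (AE") or SAE, then "the participant will have appropriate follow-up assessments and if necessary, referrals will be made for medical care". AEs still open are to be closed at Week 10.
- Section 13.2, for pregnancy: "Approximately 30 days after being withdrawn or having a positive pregnancy test, the research staff will call the" participant to confirm the due date, with a further enquiry after delivery.
- The end of section 12.1: participants who choose to leave are asked to come in to hand back product and collect payment.

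Section 17.2 bases the safety evaluation on everyone dispensed SREC. It sets reporting of unexpected, possibly related SAEs from consent until 4 weeks after product use ends. It describes active ascertainment as visit-based: "The occurrence of AEs will be sought by non-directive questioning of the participant at each visit during the study".

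**The concern.** The stop rules in 12.2 and 12.3 are unqualified, while 17.2 defines a safety window that outlasts product use by 4 weeks. For a participant withdrawn by the investigators with no AE and no pregnancy, nothing in the plan links the two. After the withdrawal visit, an event in that window reaches the study only if the participant reports it unprompted. A completer is asked directly at the remote Week 10 visit.

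Two things are at stake. The first is participant safety: these people were given SREC, most of them will not have stopped smoking, and section 13.1 itself names dual use as a risk and says the health effects of e-liquid constituents are not fully understood. The second is the safety summary: the AE percentages planned in 17.2, over everyone dispensed SREC, would combine active enquiry after product stop for completers with passive reporting for those who failed to switch.

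**Working it through.** **Step 1. Who is covered after withdrawal.** Setting the provisions side by side:

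| Participant | Provision | Contact after withdrawal |
|---|---|---|
| Discontinued for an AE/SAE, or with an open AE | 12.1 | Follow-up; open AEs closed at Week 10 |
| Pregnant | 13.2 | Call at about 30 days, and after delivery |
| Leaves by choice | 12.1 | Ambiguous: follow-up assessments if the AE condition attaches only to investigator discontinuation; otherwise only the product-return request |
| Withdrawn by investigators, no AE, no pregnancy | 12.2, 12.3 | None scheduled |

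The ambiguity in the third row does not help the fourth. The 12.1 trigger has two limbs: the participant withdraws, or the investigators discontinue because of an AE/SAE. A non-quitter removed by the study meets neither. Elsewhere in section 12.1 the plan uses the passive form for study action and an active form for participant choice.

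**Step 2. Timeline.** Inputs: product use ends at Week 6 for completers, with follow-up at Week 10 (sections 5.1 and 5.2); the Week 10 visit window is −1/+3 days, and both the Health Changes Questionnaire and the Adverse Events Scale are scheduled there (Table 3); the SAE window is 4 weeks after last use (17.2).

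- Completer: last use on day 6 × 7 = 42; Week 10 is day 70; 70 − 42 = 28 days. With the visit window, 27 to 31 days. Scheduled AE enquiries after last use: **1**.
- Week-2 withdrawal, assuming last use at that visit: last use on day 14; the SAE window ends on day 14 + 28 = 42. Scheduled AE enquiries after day 14: **0**.
- If Week 10 were kept for that person, it would fall 70 − 14 = 56 days (8 weeks) after last use, 28 days after the window closes.

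If the participant goes on using leftover product, the window moves later but no contact is added.

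**Step 3. How many.** The documents give no withdrawal rate. Section 5.3 recruits up to 120 for screening and aims for 30 compliant completers, so non-completers number at most 120 − 30 = 90. That count includes people who failed screening and never received SREC.

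For illustration only, suppose a fraction f of those dispensed SREC is withdrawn for non-cessation and the rest complete. With C completers, the number withdrawn is C/(1 − f) − C, with C/(1 − f) rounded up:

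| C | f = 10% | f = 25% | f = 50% |
|---|---|---|---|
| 20 | 23 − 20 = 3 | 27 − 20 = 7 | 40 − 20 = 20 |
| 30 | 34 − 30 = 4 | 40 − 30 = 10 | 60 − 30 = 30 |

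The values of f are assumptions. The 50% borrows the upper figure that section 15.1 gives for non-compliance, which is not a withdrawal rate.

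**The case against.** The strongest reply is that this is a narrow gap and no rule is broken. Section 17.2 says what must be reported and does not promise active contact. Spontaneous reports are expressly allowed there, and section 19.1 asks participants to report suspected injuries promptly. A week-2 non-quitter has been asked about AEs at the week 1 and week 2 visits, so exposure up to withdrawal is covered, and any AE found then brings follow-up under 12.1. The study has a single arm and AEs are only tabulated, so no comparison is biased. Early withdrawals already differ from completers in exposure and in number of enquiries. The consent pages are not available, so what participants are told about reporting after withdrawal cannot be judged.

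All of that stands, and it limits the severity. None of it puts a scheduled contact in the window.

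A second reply is that Week 10 may be meant for withdrawn participants too: 12.1 uses it to close open AEs, and section 5.2 does not restrict it to completers. The Health Changes Questionnaire asks about the time since the last visit, so a Week 10 contact would look back over the missed weeks. But section 12.3 rules out further procedures without qualification, and the only stated use of Week 10 after withdrawal is for AEs already open. If the broader reading is intended, 12.1 and 12.3 conflict, and the same amendment is needed.

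**Conclusion.** The point holds. As written, an AE-free, non-pregnant participant withdrawn by the investigators has 0 scheduled safety enquiries after product stop, against 1 for a completer, although 17.2 keeps both in the same safety population and sets the same 4-week window for both. The timeline assumes that last use coincides with the week 2 visit. That this group is chiefly non-quitters is an inference: the plan gives no split of withdrawal reasons, but failure to quit by week 2 is its one routine mandatory trigger. The number affected cannot be derived from the documents, and no event rate after withdrawal is available.

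Events before withdrawal are retained, and the primary endpoint and power are unaffected. This is a weakness in safety ascertainment that should be corrected because the correction is cheap; it does not threaten the main results.

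**What to change.** Reword 12.2 and 12.3 so that biomarker and other research collection stops at withdrawal, while AE/SAE follow-up under 12.1 and pregnancy follow-up under 13.2 continue. Add one remote contact about 4 weeks after last SREC use, with the Health Changes Questionnaire and the Adverse Events Scale, for every withdrawn participant who was dispensed SREC, unless they decline.

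The cost is a protocol amendment and one short call per withdrawn participant: at most 90 if the goal of 30 completers is met, and fewer once screen failures are removed. Week 10 is already remote and already uses both instruments, so no new staff, samples or invasive procedures are needed.

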13.0 Risks to Participants

13.1 Foreseeable Risks

PROTOCOL TITLE: Biomarkers in SREC Users

VERSION DATE: 03/13/2024

The foreseeable risks for this study are minimal. Potential risks for all participants include: emotional discomfort, breach of confidentiality, nicotine withdrawal symptoms, effects of returning to regular smoking, effects of smoking the SREC e-cigarettes, risks associated with smoking, risks to fetuses, and changes in blood pressure/heart rate and pain/bruising at the site of the phlebotomy.

1. Survey Questionnaires: The interviews will include questions about medical history, drug and alcohol use, and questionnaires about mood. Answering these personal questions could make the subject feel uncomfortable.
2. Breach of Confidentiality: The risk of the interview is loss of privacy if other people find out the results.
3. Obtaining Blood Pressure: The blood pressure cuff may cause minimal discomfort. In obtaining blood pressure, researchers may find out the subject has abnormal blood pressure and must refer them to their primary care physician.
4. Smoking Cigarettes: All cigarettes are detrimental to a person's health and can lead to severe or fatal medical problems including:
 - a. Cardiovascular Diseases: Coronary heart disease, heart attack, stroke, peripheral vascular disease, reduced blood circulation, abdominal aortic aneurysm
 - b. Respiratory Diseases: Emphysema, bronchitis, tuberculosis and chronic airway obstruction
 - c. Cancers: Lung, bladder, liver, colon, cervical, esophageal, kidney, larynx, mouth, pancreatic, throat, stomach cancers and acute myeloid leukemia
 - d. Diabetes
 - e. Immune function, rheumatoid arthritis
 - f. Other Health Risks Associated with Smoking: Including but not limited to infertility, ectopic pregnancy, lower bone density in postmenopausal women, hip fracture in women, male sexual dysfunction; age-related macular degeneration, blindness and cataracts
5. Use of SREC e-cigarette: The side effects of SREC may be similar to other commercially available vaping devices. Such devices can expose users to several chemicals, including nicotine, carbonyl compounds, and volatile organic compounds, known to have adverse health effects. The health effects and potentially harmful doses of heated and aerosolized constituents of e-liquids, including solvents, flavorants, and toxicants, are not completely understood. E-cigarette aerosol is not harmless "water vapor" although it generally contains fewer toxicants than combustible tobacco products. Specific potential known risks include:
 - a. Refill pods that will be used in this study contain nicotine. Nicotine is an addictive chemical. It is possible that this experience could lead to long-term use of e-cigarettes after the trial is over.
 - b. Nicotine may contribute to some of the disease associated with smoking
 - c. The most common side effects related to e-cigarette use are changes in taste, mucus in throat/sinus, dry mouth, dry cough, throat irritation, sore

throat, mouth ulcers, dizziness, headache, and nausea, difficulty breathing, heart palpitations, vomiting, abnormal heart rate, stomach discomfort, rash, chest pain.

- d. Although uncommon, batteries from e-cigarettes have exploded/ignited and injured users.
- e. E-cigarettes can overheat and present a minor burn risk if the button is turned on repeatedly.
- f. Ingestion of e-liquids containing nicotine can cause acute toxicity and possible death if e-liquids containing nicotine are consumed. Participants will be directed to keep device and all e-liquid refill cartridges away from pets and children.
- g. On rare occasions, allergic reactions have occurred after using e-cigarettes.
- h. Severe lung disease has been associated with using e-cigarette/vaping products. The CDC and FDA continue to investigate, but the majority of cases have involved the use of cannabis oil, such as THC, obtained on the black market. In addition, one of the chemicals of concern is the addition of Vitamin E acetate to e-liquid cartridges and pods.

6. Dual Use of Tobacco or Nicotine Products: There is also the chance of use of more than one product (e.g., continued smoking among participants) and/or continued use of the products. Cessation of all tobacco products will be strongly recommended to the subjects both at the end of the experimental phase and at follow-up.

7. Smoking Withdrawal: Participants may experience smoking withdrawal symptoms during this study. The symptoms can be uncomfortable but are typically of minimal risk. Smoking withdrawal symptoms include:

- a. Anger, irritability, frustration
- b. Anxiousness, nervousness
- c. Depressed mood or sadness
- d. Desire or craving to smoke
- e. Difficulty concentrating
- f. Increased appetite, hunger or weight gain
- g. Insomnia, problems sleeping or awakening at night
- h. Restlessness
- i. Impatience
- j. Constipation
- k. Dizziness
- l. Coughing
- m. Dreaming or nightmares
- n. Nausea
- o. Sore Throat

8. Returning to Regular Smoking: It is possible that if participants return to smoking their usual brand of cigarette at the end of the study they may experience mild and transient nausea, dizziness, and lightheadedness.

9. Changes in Blood Pressure and/or Heart Rate: Smoking and nicotine can affect the cardiovascular system which may result in changes in blood pressure and/or heart rate.
10. Changes in Mood, Emotions and Psychiatric Symptoms: Smoking and nicotine can affect a person's mood and emotions and are associated with psychiatric disorders including major depressive disorder, general anxiety disorder, bipolar disorder and eating disorders. Any changes in nicotine use or cigarette consumption could adversely affect mood, emotions and the symptoms related to psychiatric conditions in some individuals.
11. Risk to Fetus: Smoking during pregnancy can lead to miscarriage, preterm delivery, stillbirth, low birth weight, problems with the placenta, birth defects such as cleft palate, sudden infant death syndrome (SIDS), early childhood behavioral problems, altered lung development and possible propensity for addiction. Although unknown, similar effects could occur with the use of vaping devices.
12. Smoking and Oral Contraceptives in Women: Women who smoke and are over the age of 35 should not take oral contraceptives that contain estrogen without consulting their physician. Smoking while using oral contraceptives can increase the risk of having a cardiovascular event such as a heart attack or stroke. Additionally, there is a potential risk of thrombosis associated with hormonal therapy (including contraceptives) and smoking.
13. Smoking and Medications: Quitting smoking can greatly benefit participants' health. However, changes in smoking can lead to changes in how well some medications work. Participants should disclose all medications they are taking. We also recommend that participants discuss any planned or actual changes in how much they smoke with their doctor, especially if they are taking any medications for psychiatric, cardiovascular, or other serious diseases.
14. Unforeseen risks: There may be additional unforeseen short and long-term risks of participation.

Because smoking causes a multitude of diseases, if at any time the smoker wants to quit smoking, this decision will be encouraged and supported. At the end of study participation, subjects will be strongly encouraged to stop use of all tobacco products and to set a quit date and provided with a treatment resources and referral to different treatments.

13.2 Reproduction Risks:

Pregnant women will not be recruited. If participants choose to be sexually active, they should use an appropriate "double barrier" method of birth control (such as female use of a diaphragm, intrauterine device (IUD), or contraceptive sponge, in addition to male use of a condom) or the female should be using prescribed "birth control" pills, injections, or implants. Female participants with child-bearing potential will be tested for pregnancy at the baseline visit and monthly thereafter, if applicable. If a participant becomes pregnant during the study, she will be withdrawn from the study. Approximately 30 days after being withdrawn or having a positive pregnancy test, the research staff will call the

participant to confirm her due date. The licensed medical professional will follow-up with the participant after delivery to ask questions about the baby's health.

13.3 Risks to Others:

Second-hand exposure from SREC or usual brand cigarettes may be a risk to others.

